9.1.2 Randomization and Blinding

See Section 3.1

9.1.3 Stratification Factors

We will create two sets of 10 housing sites balanced on preexisting variables describing relevant characteristics of sites and their residents, e.g., property size, current smoking-related policies, and geographic location.

9.1.4 Accrual Estimates

We anticipate recruiting all 400 participants within 1 year.

9.2 Interim Analyses and Stopping Rules

Not applicable

9.3 Statistical Analysis Plans

Descriptive analyses and missing data. We will estimate means and proportions, variation, and confidence intervals for demographic and other covariates. We will consider relevant biological variables of age, sex, and race/ethnicity. We will examine patterns of smoke-free home adoption and cessation behaviors at each visit to assess whether quitting took place in the context of voluntary adoption of a smoke-free home. We will determine whether participant baseline characteristics are independent of intervention group assignment (randomization check) and attrition (attrition analysis). Missing data will be accommodated by multiple imputation.¹⁰³⁻¹⁰⁵

9.3.1 Analysis Populations

Not applicable

9.3.2 Primary Analysis (or Analysis of Primary Endpoints)

The primary outcome is self-reported voluntary adoption of smoke-free homes for ≥ 90 days at 6 months follow-up. Primary analyses include intention-to-treat comparisons. The 3-level data structure—including PSH housing site, residents, and repeated assessments—will be accommodated by mixed logistic models with random intercepts for sites and residents. The primary outcome will be a binary indicator of adopting a smoke-free home which, in an intention-to-treat analysis, will be regressed onto indicators of experimental groups, categorical time (baseline, 3 months, 6 months), and the group-by-time interaction. Any significant intervention group main effect at follow-up and group-by-time interaction effect will be interpreted and described. If any key demographic or risk factors are imbalanced at baseline, we will include a propensity score-based adjustment.¹⁰⁶⁻¹⁰⁸

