Study procedures for PSH staff participants. Eligible PSH staff participants include service staff (e.g., case managers), who are ≥ 18 years of age, are willing to engage in a 2-hour training, and are able to provide informed consent. Staff in each site will be contacted via email, and invited to participate in a 2-hour training. Study staff will screen PSH staff for eligibility, obtain written informed consent using the teach-to-goal method,⁷⁸ and offer dates for the training.

Randomization and allocation. We will randomize 20 PSH sites into intervention and waitlist control arms. We will use the method of restricted randomization—commonly applied in cluster-randomized trials with small numbers of clusters—to ensure an acceptable level of balance across groups at baseline.⁷⁶ First, we will create two sets of 10 housing sites balanced on preexisting variables describing relevant characteristics of sites and their residents, e.g., property size, current smoking-related policies, and geographic location. Second, we will randomly assign one set of sites to intervention and the other to the wait-list control.

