9.1 Sample Size Considerations

9.1.1 Sample Size and Power Estimate

Our study is powered to assess both the primary outcome of smoke-free home adoption ≥ 90 days and the secondary outcome of point prevalence abstinence at 6-months follow-up. We designed the RCT to detect medium-large effect sizes, which are consistent with estimates from our pilot study¹⁴ and from other studies of brief interventions to increase adoption of smoke-free homes (intervention effect $\geq 40\%$ versus control effect $\sim 25\%$).^{32,139} Power analyses assumed 80% power; two-tailed alpha of 0.05; N=400 smoking residents recruited from 20 PSH units; 80% retention at 6-months; average 6-month site cluster size of 16 residents; group comparisons of 6-month binary outcomes describing adoption of a smoke-free home for ≥ 90 days and point prevalence abstinence from preliminary data, expected 6-month control group outcome rates of 12% and 4% for smoke-free home adoption and point prevalence abstinence, respectively; from preliminary data, intra-site outcome correlations of 0.077 (ρ_{SFH}) and zero (ρ_{PPA}); and mixed logistic models including random intercepts for sites. Estimated design effects equaled $1+(16-1)\rho_{SFH}=2.16$ and $1+(16-1)\rho_{PPA}=1.0$, respectively. For the primary outcome of voluntary smoke-free home adoption, the minimum detectable effect for the intervention group is 30.3% compared to 12% for the control group, which compares favorably with 31.3% obtained in our pilot study as well.¹⁴ For the secondary outcome of point prevalence abstinence at 6 months, the minimum detectable effect in the intervention group is 12.6% compared to 4% in the control group, which compares favorably with 16.9% obtained in the pilot study.¹⁴

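### The primary model holds each site's effect constant across visits, so its group-by-time test is anti-conservative if site effects move; the 6-month arm contrast is affected less

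*Combined protocol and SAP*

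**What the plan says.** Housing sites are the unit of randomisation. After two balanced sets of 10 are formed, section 3.1 states: "we will randomly assign one set of sites to intervention and the other to the wait-list control".

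Section 9.1.1 sizes the trial on a comparison of 6-month binary outcomes with "N=400 smoking residents recruited from 20 PSH units", "80% retention at 6-months", an "average 6-month site cluster size of 16 residents" and a "two-tailed alpha of 0.05". It applies a within-site correlation of 0.077 in full, as a design effect of 2.16.

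Section 9.3.2 regresses adoption on group, three-level time and their interaction. The structure of sites, residents and visits "will be accommodated by mixed logistic models with random intercepts for sites and residents". On which result counts, it says: "Any significant intervention group main effect at follow-up and group-by-time interaction effect will be interpreted and described". Sections 9.1 and 9.3 give no site-by-visit random effect, site-level random slope, cluster-robust variance or small-sample degrees of freedom.

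**The concern.** A site intercept that takes the same value at every visit drops out of any comparison of change. The group-by-time test is then judged against variation within residents only. If a whole site shifts between visits, the model counts that shift as separate evidence from each of about 16 residents. In a trial that randomises sites and measures them repeatedly, the error term for group-by-time should include site-by-time variation, and this model has none.

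The sizing and the analysis also disagree. Section 9.1.1 charges the whole within-site correlation at 6 months, while the interaction test charges none of it. Because 9.3.2 lists the interaction among the results to be interpreted, a few drifting sites could produce a reported effect with an interval that is too narrow.

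Site-specific shifts are plausible from the protocol itself. Staff are trained site by site (5.1), study procedures follow each site's COVID-19 rules (1.4), and residents are asked how COVID-19 changed smoking rules at home (7.1).

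**Working it through.** **1. Reproducing the plan's figure.** Design effect = 1 + (16 - 1) x 0.077 = 2.155. Analysed per arm = 200 x 0.80 = 160, so the effective number is 160 / 2.155 = 74.2. With 12% in controls and unpooled variance, the standard error at 30.3% is sqrt[(0.12 x 0.88 + 0.303 x 0.697) / 74.2] = 0.0653. Then 0.12 + (1.960 + 0.842) x 0.0653 = 0.303. The stated 30.3% is reproduced, so the sizing does carry the full site correlation at 6 months.

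**2. Linear check of the mechanism.** Set total outcome variance to 1. Let r be the between-visit correlation of a site's effect and c the correlation of a resident's own residual over time. Neither is in the documents; both are assumptions.

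- Site-by-visit variance: s = 0.077 x (1 - r)
- Within-resident variance: e = 0.923 x (1 - c)
- True variance of an arm's mean change is proportional to s/10 + e/160; the planned model uses about (s + e)/160
- Ratio of true to modelled variance = (16s + e) / (s + e); actual level = P(|Z| > 1.96 / sqrt(ratio))

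| r | c | s | e | ratio | actual level |
|---|---|---|---|---|---|
| 1.0 | any | 0 | any | 1.00 | 5.0% |
| 0.8 | 0 | 0.0154 | 0.923 | 1.25 | 7.9% |
| 0.8 | 0.5 | 0.0154 | 0.4615 | 1.48 | 10.8% |
| 0.5 | 0 | 0.0385 | 0.923 | 1.60 | 12.1% |
| 0.5 | 0.5 | 0.0385 | 0.4615 | 2.16 | 18.2% |

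**3. Simulation of the planned logistic model under no effect.** Settings: 10 sites per arm; 20, 17 and 16 residents per site at the three visits (17 is assumed); 12% at 3 and 6 months; total site variance set to a correlation of 0.077. The model of 9.3.2 was fitted by Gauss-Hermite maximum likelihood, with 600 to 1,000 trials per setting. Resident variance on the logit scale was assumed to be about 0, 3 and 8 for the 12% baseline and 3 for the 2% baseline. Rejection rates at nominal 5%:

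| Test | r = 1.0 | r = 0.8 | r = 0.5 | r = 0 |
|---|---|---|---|---|
| Baseline 12%: interaction, 2 df | 3-5% | 9-14% | 18-23% | 27-38% |
| Baseline 12%: baseline-to-6-month interaction, 1 df | 3-5% | 8-11% | 13-18% | 21-26% |
| Baseline 12%: 6-month arm contrast | 7-9% | 7-9% | about 10% | 12-14% |
| Baseline 2%: interaction, 1 df, Wald | 2% | 4% | 6% | 7% |
| Baseline 2%: interaction, 1 df, likelihood ratio | 6% | 8% | 11% | 14% |
| Baseline 2%: interaction, 2 df, Wald | 3% | 6% | 11% | 17% |
| Baseline 2%: interaction, 2 df, likelihood ratio | 8% | 11% | 18% | 24% |

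A t-test on the 20 site-level changes (18 df) rejected in 3-6% of trials in every setting.

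A second simulation used 16 residents per site at every visit, flat 12% rates or a shared 12-20-25% rise, and 1,500 trials per setting. For r = 1.0, 0.8 and 0.5 the 2-df interaction rejected in about 4%, 9-12% and 16-22%, and the 6-month contrast in 7-9%, 8-10% and 10-12%.

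**4. Why the 6-month contrast is above 5% even with constant site effects.** A 1.96 cutoff on a statistic with 18 df rejects in 6.6% of trials. If maximum likelihood also shrinks the site variance by 18/20, the effective cutoff is 1.96 x sqrt(0.9) = 1.86, which rejects in 7.9%. That accounts for the 7-9%. What the omitted term adds is smaller. With resident variance 3, the true total site variance was 1.39, and its median estimate fell from 1.12 at r = 1.0 to 0.65 at r = 0.5, because the model keeps only the part of the site effect shared across visits.

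**The case against.** The strongest reply is that the size rests on a quantity the documents do not give. Section 9.1.1 reports one within-site correlation, at one visit. If site effects are stable, the interaction test holds its level. A reader might infer from the structure alone that the planned test runs at two to four times its nominal level. The documents do not support that as an unconditional statement: it needs a between-visit correlation of roughly 0.5 to 0.8 and a 12% baseline.

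The 12% baseline is itself doubtful. It is the pilot's figure (1.2), whereas 4.1.1 admits only residents who smoke at home, so baseline adoption should be near zero. At 2% the 1-df Wald test is hardly inflated. The likelihood-ratio test remains high, but part of that is small-sample error, since it is already 6-8% with constant site effects.

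A reader might also infer that the primary analysis ignores clustering altogether. It does not: the site intercept enters the 6-month arm contrast, which matches the stated primary outcome and the sizing. The excess there is modest, and part of it comes from the normal reference.

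Finally, blocks of two intervention and two control sites (4.2) and balanced allocation (3.1) should tend to even out regional or calendar shocks. Shifts common to all sites go into the time effect, so only site-specific drift matters.

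All of this limits the size. It does not supply the missing variance term or justify the unstated assumption of constant site effects, and the interaction remains a result that 9.3.2 says will be interpreted.

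**Conclusion.** The structural point stands on the text: the group-by-time test in 9.3.2 has no site-by-visit error term and is anti-conservative if site effects move between visits.

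The size is conditional. At 12% baseline adoption, the interaction tests run at about 8-14% for a between-visit correlation of 0.8 and 13-23% for 0.5, against 3-5% for constant site effects. At 2% baseline and the same two correlations they run at about 4-11% (Wald) or 8-18% (likelihood ratio). Taking both simulations together, the 6-month contrast runs at about 7-10% and 10-12%, against 7-9% for constant site effects.

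Nothing in the documents shows that site effects will drift, or by how much. This is a should-fix point: confidence is high in the mechanism and medium in the size of the inflation.

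**What to change.** In section 9.3.2:

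- Name the 6-month arm contrast as the primary test, with group-by-time as supporting.
- Add a random site-by-visit intercept to the site and resident intercepts, and keep it even if its variance is estimated as zero, so that the model is not chosen from the data.
- Use degrees of freedom based on the 20 sites: 18 for the 6-month contrast. Without this, the 7-9% seen with constant site effects would remain.
- Pre-specify a t-test on the 20 site-level 6-month proportions (18 df), to be used only if the model does not converge.

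In the linear check, a site-by-visit component brought the level back to about 5-6%. The full logistic model with this term was not simulated, so the sponsor should confirm its level and convergence before the analysis.

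The cost is a short amendment, one more variance component and somewhat wider intervals. The 18-df reference alone widens them by about 2.10 / 1.96 = 1.07, or 7%, and more is added where site effects do shift. No new data or participants are needed, and the analysis would then charge the site correlation at 6 months as section 9.1.1 already does.

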3.2 Sample Size

We will recruit 400 PSH resident participants, with 200 each in the intervention and wait-list control arms (~20 participants per site). We expect to enroll 100 PSH staff, approximately 5 staff per site.

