4.1 Eligibility Criteria

4.1.1 Inclusion Criteria

In order to be eligible to participate in this study, an individual must meet all of the following criteria:

1. Age 18 years or older
2. Ability to understand study procedures and to comply with them for the entire length of the study.
3. Ability of individual or legal guardian/representative to understand a written informed consent document, and the willingness to sign it.
4. Current smokers [(smoked at least 100 cigarettes in lifetime, daily or non-daily smoking in the past 7 days and at least 5 cigarettes per day, verified by expired Carbon Monoxide (CO) \geq 8 parts per million (ppm)]⁷⁷ who smoke in their homes.
5. Expect to live in the PSH site for at least 12 months, and
6. English proficient.

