4.2 Recruitment Methods

Recruitment schedule. We will recruit 400 PSH resident participants, with 200 each in the intervention and wait-list control arms (~20 participants per site; Figure 6, Table in Recruitment and retainment section in human subjects). Within each site, all resident participants will be informed about the study and invited to participate. We will recruit participants within blocks of four housing sites per month, with each block containing two intervention and two wait-list control sites, and anticipating roll-out of one such block per month. We anticipate completing recruitment and enrollment of all participants in 6 months, allowing for a one-to-two-month extension to complete these activities. We will offer the intervention to the wait-list control participants once all participants in the intervention sites from the same block have completed their 6-month follow-up. We expect to enroll 100 PSH staff. We will obtain information on the total number of residents and staff at each site to provide an estimate of the proportion enrolled in the intervention.

Within each site, study staff will advertise the study to residents the week prior to enrollment by placing flyers at the study site and making announcements at community meetings. After the informational meeting, study staff will be present at the recruitment sites during designated times to screen interested participants for eligibility and enroll those eligible into the study. Study staff will describe the purpose of the study, the study procedures, including risks and benefits, and obtain written informed consent using the teach-to-goal method at the time of eligibility.⁷⁸ Participants will complete the baseline questionnaire and will receive the study staff-delivered intervention within one week of enrollment. We have adjusted the timeline for recruitment, intervention delivery and follow-up to account for extra time that we may need to complete study procedures to follow protocols around social distancing that PSH sites may have put in place due to COVID-19.

Data collection reimbursements. We will reimburse all resident participants with [REDACTED] gift cards for completing the baseline questionnaire, [REDACTED] the 3-month questionnaire and [REDACTED] the 6-

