PSH resident measures. Demographics. We will obtain information on age, sex (sex assigned at birth, current gender), race/ethnicity, education, income from all sources, marital status, and number of smokers in the household. Social determinants of health. We will obtain information on unmet subsistence needs (insufficient access to food, clothing, utilities),⁸¹ social and instrumental support,^{82,83} lifetime history of homelessness, length of stay in current residence, other housing circumstances (e.g., loss of housing), and exposure to urban life stressors.⁸⁴ Alternative tobacco, nicotine product and cannabis use. We will assess ever and past 30-days use and indoor use of e-cigarettes, cigars/little cigars, smokeless tobacco, pipe tobacco, hookah, blunts, and cannabis. Nicotine dependence and smoking cessation. We will assess Fagerstrom's test for nicotine dependence⁸⁵ craving⁸⁶, impulsivity⁸⁷, cigarette smoking behaviors, cigarette quit attempts (ever, in the past year, and since the last visit), length of the last quit attempt, longest time abstinent, and use of cessation aids.⁸⁸ Smoke-free policy measures.⁹ We will assess knowledge of current no-smoking policies, frequency of past-month exposure to SHS, attitudes toward smoke-free policies and indoor cannabis use, knowledge and skills related to smoke-free home adoption, and barriers to smoke-free home adoption.⁹ Measures related to voluntary smoke-free home adoption.^{9,14} We will ask whether participants adopted a smoke-free home voluntarily in the past 90 days and the length of the last adoption, which will be used to define our primary outcome. We will ask those who reported a smoke-free home when they last smoked in their home. We will ask participants to report when they adopted a smoke-free home and when they quit smoking in the past 90 days. We will assess whether they attempted to quit at the same time as they adopted a smoke-free home, adopted a smoke-free home and quit later, or adopted a smoke-free home but did not quit. Expenditures for tobacco use. We will obtain information on the amount of money spent on tobacco in the past week, which we will use to estimate tobacco-related expenditures. Chronic diseases. We

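### The primary model treats baseline as an outcome level although eligibility makes that outcome essentially zero, and section 9.3.2 does not name the 6-month arm contrast as the single confirmatory test

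*Combined protocol and SAP*

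**What the plan says.** The primary outcome in section 9.3.2 is a self-reported smoke-free home of at least 90 days, assessed at 6 months. The model in the same section is a three-level mixed logistic regression with site and resident random intercepts. Its terms are arm, "categorical time (baseline, 3 months, 6 months), and the group-by-time interaction". The sentence that introduces the modelled variable speaks of adoption and does not repeat the 90-day condition. On inference it says: "Any significant intervention group main effect at follow-up and group-by-time interaction effect will be interpreted and described". It gives no reference coding, no single primary contrast and no multiplicity rule.

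Three other sections bear on this:

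- Section 4.1.1 restricts entry to current smokers "who smoke in their homes".
- Section 4.2 says that participants "will receive the study staff-delivered intervention within one week of enrollment".
- Section 7.1 supplies the outcome item: "We will ask whether participants adopted a smoke-free home voluntarily in the past 90 days and the length of the last adoption". Adoption of under 90 days is also distinguished at 6 months, in the air-nicotine sampling of section 6.2.3.

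Section 9.1.1 powers the comparison of the 6-month binary outcomes, using models with a random intercept for site only.

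**The concern.** A resident who smokes at home at entry has not had a smoke-free home for the previous 90 days. Under the stated definition, the baseline cell therefore holds no events, or almost none, in either arm. A logistic model cannot put a finite value on the log odds in an empty cell, nor on an arm difference between two empty cells, nor on a change measured from them. Yet the interaction in section 9.3.2 would ordinarily be read as a difference in change from baseline.

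The stake is the primary endpoint. An analyst who follows the text will meet non-convergence or huge standard errors, and must then choose a coding, a test or a set of rows with the data in hand. An interaction reported as non-significant could also be read as absence of effect when the intervention works. The plan does not say in advance which result carries the conclusion.

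**Working it through.** **Inputs from section 9.1.1 and section 3.2.** "Power analyses assumed 80% power"; "two-tailed alpha of 0.05"; 400 residents "with 200 each in the intervention and wait-list control arms"; 80% retention and 16 residents per site at 6 months, so 10 x 16 = 160 per arm; control rate 12%; intra-site correlation 0.077.

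**1. The plan's own figure.** Design effect = 1 + 15 x 0.077 = 2.155 (stated as 2.16). Effective n = 160 / 2.155 = 74.2 per arm. At 12% v 30.3% with unpooled variance, SE = sqrt[(0.12 x 0.88 + 0.303 x 0.697) / 74.2] = 0.0653. Then 0.183 / 0.0653 = 2.80, and 2.80 - 1.96 = 0.84, which is 80% power. The stated minimum detectable rate is reproduced, and it belongs to the 6-month contrast.

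**2. The baseline cell.** If the true baseline rate is p, the chance that an arm of 200 has no events (taking residents as independent) is (1 - p)^200. The chance that at least one arm has none is 1 - [1 - (1 - p)^200]^2.

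| Baseline rate | One given arm empty | At least one arm empty |
|---|---|---|
| 0 | 100% | 100% |
| 0.5% | 37% | 60% |
| 1% | 13% | 25% |
| 2% | 1.8% | 3.5% |
| 12% | about 0 | about 0 |

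**3. What an empty baseline does.** As the baseline intercept goes to minus infinity, each baseline row contributes a likelihood of 1, whatever the random effects. Those rows then carry no information on the baseline arm term or on any term measured from it. In a three-level fit to simulated data, the baseline intercept moved from -4 to -19.5 as its bounds were relaxed, and the curvature for the baseline arm term was about 0. In 200 simulated trials at 12% v 30.3%, the baseline-referenced Wald test of arm by 6 months had SE about 24,000 and p never below 0.999.

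**4. What survives.** Simulated example with no baseline events, 16 v 43 events at 3 months and 18 v 52 at 6 months, all rows kept:

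- 6-month log odds ratio 1.62 (SE 0.43), unchanged when the baseline arm effect is fixed at 0.
- Likelihood-ratio interaction statistic 0.149: p = 0.93 on the nominal 2 df. Because the baseline rows drop out, it really tests one constraint, equal 3- and 6-month effects, for which p = 0.70.

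**5. The 3-month visit.** Take 3 months as 91 days from enrolment. Counselling on day 0 to 7 leaves 91 - 0 = 91 down to 91 - 7 = 84 days. If the 90-day condition applies at that visit and the visit is on time, adoption must begin by about day 1. In an example with 1 v 0 events at 3 months and 18 v 52 at 6 months, the 3-month arm term separated (SE above 1,000) and the 6-month estimate became 3.74 (SE 2.89). The resident standard deviation reached the limit allowed in that fit. With one informative record per resident, there is almost nothing to estimate it from. This is a single example that shows instability, not a general figure.

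**6. Error rate if either result counted.** From 20,000 null simulations of site-level summaries, 10 v 10 sites:

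- 6-month contrast alone: 4.8-5.1%.
- 6-month contrast or 2-df interaction: 5.8-9.0%.
- Averaged follow-up effect or interaction: 5.8-9.6%.
- Two independent tests, for reference: 1 - 0.95^2 = 9.75%.

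The upper ends come from a 12% baseline rate. With baseline zero and 12% at both follow-up visits, either rule gave 7.7%.

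The three-level fits and the null simulations assume a site SD of 0.52 on the logit scale, a resident SD of 1.5, and 16 residents per site at every visit. The documents do not give these SDs or the baseline and 3-month rates used.

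**The case against.** The strongest reply is that the arm comparison is not lost. A group-by-time model contains the 6-month contrast whatever the reference level, section 9.3.2 mentions an arm effect at follow-up, and section 9.1.1 powers that comparison. This stands. A reader might infer that the primary analysis cannot be estimated, or has no power. The documents do not support that: the near-1 p-values belong to a baseline-referenced Wald test, which section 9.3.2 does not specify.

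A reader might also infer that the outcome is zero by design at 3 months. That needs the 90-day condition at that visit and attendance close to day 91. The modelled variable is worded without the condition, the schedule gives no day-level window per participant, and shorter adoption can be derived from the items collected. But if the indicator means adoption of any duration, it is not the stated primary outcome, so the text needs settling either way.

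A third tempting reading is that the plan allows two routes to success and so doubles the error rate. The sentence joins the two effects with a conjunction and promises interpretation and description. It states no success rule, and an interaction test that never rejects would add no false positives.

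The pilot's 12% baseline rate (section 1.2) does not rescue the model. At 12% all terms were estimable, but the pilot's eligibility is not given and this trial enrols people who smoke at home. Section 1.2 does define a smoke-free home as a rule, so a few residents who have a rule and break it might report adoption at baseline. Hence essentially zero, not exactly zero.

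**Conclusion.** The point holds in limited form. Given the eligibility rule and the 90-day definition, the baseline arm term and the baseline-referenced interaction terms are not identified, or barely so if a handful of residents report adoption at entry. Wald tests of them are meaningless, and a likelihood-ratio interaction test asks only whether the 3- and 6-month effects differ. The 6-month contrast is estimable and is the comparison for which the 30.3% v 12% calculation was made, but section 9.3.2 does not designate it as the single confirmatory test.

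Two parts are conditional. The 6-month estimate can become unstable if the 3-month indicator is also near zero. Type I error of about 6-10% would follow only if either result were treated as a positive finding.

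Abstinence has the same structural zero at entry (recent smoking and CO of at least 8 ppm required, against 5 ppm or less for abstinence). Section 9.3.3 specifies only a mixed logistic model, so the problem arises there only if a baseline row is included.

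This is more than missing detail: following the model as written yields an uninformative interaction test on the primary endpoint.

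**What to change.** In section 9.3.2:

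- Name one primary test: the two-sided 0.05 arm contrast on the 6-month indicator of at least 90 days, with a site random intercept. This matches section 9.1.1.
- Remove baseline as an outcome row. If a longitudinal model is kept, constrain baseline to be equal across arms. Removal is cleaner, because the constraint still leaves the baseline intercept without a finite value.
- Define the indicator used at each visit, and put 3-month adoption of any duration in a secondary repeated-measures model.
- Make the group-by-time interaction descriptive.

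Apply the same rule to abstinence if it is modelled with a baseline row.

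Keep the existing item on length of the last adoption as the source of duration. Section 7.1 also asks when the resident last smoked at home, but deriving the 90 days from that date would replace a household rule with a behaviour and so change the endpoint.

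The cost is a small amount of rewording in the analysis plan and the loss of the interaction as an inferential test. No new data are needed. Three-month answers can still inform the multiple imputation planned in section 9.3.

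### The primary model is fixed only after a baseline balance check, omits the site variables that restrict the randomisation, and names no small-sample method for 20 sites

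*Combined protocol and SAP*

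**What the plan says.** Sections 3.1 and 9.1.3 describe restricted randomisation: "We will create two sets of 10 housing sites balanced on preexisting variables describing relevant characteristics of sites and their residents". Property size, smoking-related policies and geographic location are given as examples, so the final list is open. Section 3.1 then assigns one set at random to each arm. Section 4.2 adds that sites are recruited in blocks of four, two from each arm.

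The primary model in Section 9.3.2 uses "mixed logistic models with random intercepts for sites and residents". Its fixed effects are arm, time (baseline, 3 and 6 months) and their interaction. No balancing variable and no block appears.

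Other covariates enter in one way only. Section 9.3 says "We will determine whether participant baseline characteristics are independent of intervention group assignment (randomization check", and Section 9.3.2 follows with "If any key demographic or risk factors are imbalanced at baseline, we will include a propensity score-based adjustment". Neither section says which factors count as key, what size of difference counts as imbalance, or whether the score is used for weighting, stratification or as a covariate.

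No section states a reference distribution, degrees of freedom, small-sample correction or permutation test for the arm effect. Section 9.1.1 gives the design figures: "Power analyses assumed 80% power", "two-tailed alpha of 0.05" and "N=400 smoking residents recruited from 20 PSH units".

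**The concern.** There are three linked gaps.

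1. **A model chosen from the data.** The trigger leaves at least two possible primary estimates, adjusted and unadjusted. The choice depends on a judgement made after the baseline data are available, and two competent analysts could follow the plan and report different primary results. Nor is it clear how a propensity score would represent an allocation made at site level.

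2. **Balancing variables left out.** If the variables that restrict the allocation predict the outcome, leaving them out keeps their between-site variance in the standard error although the design has already balanced it between the arms. Precision that the design bought is then not used.

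3. **Few clusters.** With 10 sites per arm, the reference distribution matters. Plan and software default could differ without anyone having decided the question.

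At stake are the power of the primary test, its type I error, and whether the primary result is reproducible from the plan.

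**Working it through.** **Inputs from the plan.** Section 9.1.1: two-sided alpha 0.05, power 80%, 20 sites, 80% retention, 16 analysed residents per site, control rate 12%, intra-site correlation 0.077, stated detectable rate 30.3%. Section 3.2: 200 residents per arm, so 200 × 0.80 = 160 analysed per arm.

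**Input not in the plan (assumption).** R², the share of between-site variance explained by the balancing variables. Range shown: 0, 0.3 and 0.6.

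**Step 1: reproduce the plan's figure.**
- Design effect = 1 + (16 − 1) × 0.077 = 2.155 (the plan gives 2.16).
- Effective n per arm = 160 / 2.155 = 74.2.
- Standard error at 30.3% = √[(0.12 × 0.88 + 0.303 × 0.697) / 74.2] = 0.0653.
- Standardised effect = (0.303 − 0.12) / 0.0653 = 2.80.
- Power with z = Φ(2.80 − 1.96) = 80.0%, so the detectable rate is 30.3%. It matches exactly (unpooled variance, z = 1.96). The pooled version gives 30.7%.

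**Step 2: same calculation, t reference on 20 − 2 = 18 df.**
- Critical value 2.101 in place of 1.960.
- Power at 30.3% (noncentral t) = 75.5%; detectable rate = 31.5%.
- Using 1.96 where t on 18 df applies gives a type I error of 6.6%.

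**Step 3: three site-level terms added, 15 df, none prognostic (R² = 0).** Detectable rate = 31.8%.

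**Step 4: simulation of the 6-month comparison.** Twenty sites of 16, marginal control rate 12%, intra-site correlation 0.077, logistic model with a site random intercept fitted by maximum likelihood, 3,000 runs per cell (Monte Carlo error about 0.4 points on type I error). Two site covariates were balanced by drawing from the best 10% of 200 candidate allocations.

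| Restricted randomisation | R² = 0 | R² = 0.3 | R² = 0.6 |
|---|---|---|---|
| Type I error, unadjusted, z | 7.8% | 5.4% | 4.0% |
| Type I error, unadjusted, t(18) | 5.9% | 4.1% | 2.6% |
| Type I error, adjusted, z | 9.0% | 8.7% | 7.9% |
| Type I error, adjusted, t(16) | 6.8% | 6.5% | 5.6% |
| Power at 30.3%, unadjusted, t(18) | 72% | 72% | 75% |
| Power at 30.3%, adjusted, t(16) | 75% | 82% | 89% |

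**Step 5: is the power gain only an artefact of the adjusted test rejecting too often?** Repeat Step 2 with the correlation scaled by (1 − R²) and 16 df. At R² = 0.3 the design effect is 1 + 15 × 0.077 × 0.7 = 1.809 and power at 30.3% is 81.9%. At R² = 0.6 it is 1 + 15 × 0.077 × 0.4 = 1.462 and power is 89.1%. This formula holds the test at 5% and agrees with the simulation. At R² = 0 the same formula gives 74.9%, slightly below the 75.5% of Step 2, so the 3-point simulated gain in that column should not be counted as real.

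**The case against.** **The plan does not say that z tests will be used.** A reader might infer from Step 1 that the primary test follows normal theory. The documents do not support that. Using z in a sample-size formula is common and does not fix the analysis. The fault is silence on the method.

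**Type I error is not shown to exceed 5%.** A reader might infer that the plan both loses precision and rejects too often. Under restricted allocation the two pull against each other: the unadjusted z test rejects 7.8% when the balanced variables carry no information, but 5.4% and 4.0% when they do. Where omission costs real power, the z test is near nominal or conservative. This objection stands, and the supportable statement is that the error rate is not controlled.

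**The simulated model is not the planned one.** It covers one time point, whereas Section 9.3.2 has three, with resident intercepts. If the effect is read from the interaction, a site effect constant over time largely cancels, and both the gain from site covariates and the between-site degrees of freedom could differ. This stands as a limit on the figures. It does not supply the missing specification.

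**How often the trigger would fire is unknown.** A reader might infer that it would nearly always fire. With no factors or threshold given, that cannot be derived. If a covariate were tested at 5% ignoring site, with 20 residents per site, the chance of a false flag would be about 7% at an intra-site correlation of 0.01 and 21% at 0.077. Both the test and the covariate correlations are assumptions, and the plan's 0.077 is for the outcome only.

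**Adjustment may not pay.** If the variables are not prognostic, adjusting costs degrees of freedom for nothing. That is true, but the cost is small (Step 3), and choosing variables for restriction implies that they are thought to matter.

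**Conclusion.** The concern holds as a gap in specification with a measurable cost. The primary model depends on an undefined balance check, leaves out the variables that restrict the randomisation, and names no inference method for 20 sites.

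- **Precision:** about 10 to 14 points of power at 30.3% (72% to 82%, and 75% to 89%), if the balancing variables explain 30% to 60% of between-site variance. That share is assumed, and the figures are for the 6-month comparison only.
- **Type I error:** about 4% to 8% if z tests are applied to the unadjusted model, with the direction set by how prognostic the omitted variables are. The documents support neither a claim that z will be used nor a claim that the error rate is above 5%.
- **Stated detectable rate:** 30.3% rests on z. On t with 18 df it is 31.5%, and power at 30.3% is about 75%.

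The effect of the propensity step on the error rate was not quantified, because the plan gives too little to simulate it.

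**What to change.** Amend Section 9.3.2 before analysis:

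1. Always include, as fixed covariates, the variables actually used to restrict the randomisation, and list them. Add a few baseline predictors named before the data are seen. State whether the blocks of four in Section 4.2 constrain the allocation and, if so, how the model reflects them.
2. Remove the imbalance-triggered propensity adjustment from the primary model. It may stay as a sensitivity analysis. The balance table can remain descriptive.
3. In the same change, test the arm effect with a t reference on between-site degrees of freedom (18 minus the number of site-level terms) or another named small-sample method. Adjusting without a correction gave 7.9% to 9.0% type I error, so items 1 and 3 must go together.
4. Check the chosen method by simulating the planned three-time-point model, because t on 16 df still gave 5.6% to 6.8%.
5. Restate the detectable rate in Section 9.1.1 on that basis.

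A permutation test is an option only if the allocation is drawn from a large set of acceptable allocations. Section 3.1, read literally, forms one pair of sets and so allows just two.

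The cost is wording and a simulation, with no new data or sites. A few between-site degrees of freedom are spent: three terms leave 15. Coding location by the four counties in Section 4.3.1 would take three by itself, so the coding should be kept sparse. If the variables prove not to be prognostic, the detectable rate worsens slightly, from 31.5% to 31.8% with three terms.
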